2.4 Rationale for sample size

Cohort 1: 21 subjects

Cohort 2: 20 subjects

Cohort 3: 20 subjects

[Rationale]

3. Endpoints

3.1 Pharmacokinetics

(1) Plasma concentration

Plasma concentration of unchanged MT-6548

(2) Pharmacokinetic parameters

$AUC_{0-\infty}$, C_{max} , t_{max} , AUC_{0-last} , $MRT_{0-\infty}$, Kel , and $t_{1/2}$ of unchanged MT-6548

3.2 Safety endpoints

The following endpoints should be evaluated.

(1) Adverse events and adverse drug reactions

(2) General laboratory tests

- (3) Vital signs
- (4) Standard 12-lead ECG

4. Calculation of Pharmacokinetic Parameters

For each evaluation period, plasma concentrations of unchanged MT-6548 should be measured, and pharmacokinetic parameters should be calculated by noncompartmental analysis. The time used for calculation of pharmacokinetic parameters should be the actual elapsed time with the time of administration of the study drug at 0.00 hours for each study period (round to two decimal places). If observed and predicted values exist for the same parameter, the observed value should be adopted.

4.1 Area under the plasma concentration-time curve extrapolated to infinity: $AUC_{0-\infty}$

Unit: $\mu\text{g}\cdot\text{h/mL}$

Number of display digits: Should be rounded and displayed to one decimal place.

Calculation method: $AUC_{0-\infty} = AUC_{0-t} + C_{obs}/K_{el}$

Where AUC_{0-t} is the area under the plasma concentration-time curve from before administration to the last observation point, which is not below the lower limit of quantification (Linear Trapezoid [Linear Interpolation]), C_{obs} is the concentration at the last observation point, and K_{el} is the elimination rate constant of the terminal elimination phase in the elimination phase. If K_{el} is not calculated, it should be regarded as a missing value and displayed as “—”.

4.2 Maximum plasma concentration: C_{max}

Unit: $\mu\text{g/mL}$

Number of display digits: Same as the measured value (however, the units should be converted from ng/mL to $\mu\text{g/mL}$).

Calculation method: The measured value showing the highest plasma concentration in each subject should be used. If the concentrations are below the lower limit of quantification at all time points, the concentration should be 0.000 $\mu\text{g/mL}$. If the values measured at all time points are not adopted, they are regarded as missing values and displayed as “—”.

4.3 Time to reach maximum plasma concentration: T_{max}

Unit: h

Number of display digits: Should be displayed to two decimal places.

Calculation method: The time point showing the highest plasma concentration in each subject is used. If the C_{max} value is at least two time points, the first time point should be taken as t_{max} . If the plasma

concentrations are below the lower limit of quantification at all time points, they should be regarded as missing values and displayed as “—”.

4.4 Area under the plasma concentration-time curve up to the last measurement time point: $AUC_{0-\text{last}}$

Unit: $\mu\text{g}\cdot\text{h/mL}$

Number of display digits: Should be rounded and displayed to one decimal place.

Calculation method: The area under the plasma concentration-time curve from baseline to the last measurement time point is calculated using the trapezoidal method (Linear Trapezoid [Linear Interpolation]).

If the concentrations are below the lower limit of quantification at all time points, the concentration should be $0.0 \mu\text{g/mL}$.

4.5 Mean residence time extrapolated to infinity: $MRT_{0-\infty}$

Unit: h

Number of display digits: Should be rounded and displayed to two decimal places.

Calculation method: $MRT_{0-\infty} = AUMC_{0-\infty}/AUC_{0-\infty}$

However, $AUMC_{0-\infty}$ is the first moment of $AUC_{0-\infty}$; and if K_{el} is not calculated, it should be regarded as missing value and displayed as “—”.

4.6 Elimination rate constant of the terminal elimination phase: K_{el}

Unit: /h

Number of display digits: Should be rounded and displayed to four decimal places.

Calculation method: This is the slope of the regression line when the linear regression of logarithmic concentration against time is performed for the terminal elimination phase of the concentration curve. However, it should be calculated only if there are ≥ 3 points traced back from the last time point when plasma concentrations are detectable without including C_{max} , and the number of trace points with the highest R^2 of linear regression should be adopted. It should be regarded as missing and “—” is displayed if ≤ 2 points.

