4.7 Terminal elimination half-life: $t_{1/2}$

Unit: h

Number of display digits: Should be rounded and displayed to two decimal places.

Calculation method: $t_{1/2} = \ln(2)/K_{el}$

It should be calculated for only subjects with a calculated K_{el} . If K_{el} is not calculated, it should be regarded as a missing value and displayed as “—”.

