7.3 Handling of PK-related data

The permitted range of blood sampling for plasma concentration measurement is set as shown below, in consideration of the range of working hours for puncture, etc. Data outside the permitted ranges should not be imputed. Details of the acceptance or rejection of drug concentration data used for the

tabulation of drug concentration data and the calculation of pharmacokinetic parameters and the handling of other drug concentration data should be decided in the review of handling of drug concentration data and described in the final version of the statistical analysis plan.

- Immediately before study drug administration: Within 30 minutes before the specified time
- 0.5 to 16 hours after study drug administration: Within ± 5 minutes of the specified time
- 24 hours after study drug administration: Within ± 15 minutes of the specified time

(1) **Rejected data**

They will not be included in the calculation of summary statistics or pharmacokinetic parameters at each time point of blood sampling.

(2) **Plasma MT-6548 concentrations (units should be converted from ng/mL to μ g/mL)**

1) “NS”: No data

Should be treated as a missing value.

2) “<LLOQ”: Below the lower limit of quantification (0.1 μ g/mL)

Should be treated as 0.000 μ g/mL.

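### SAP 4.6 defines Kel as the slope of log concentration on time and omits the minus sign that the formulas for AUC0-inf, MRT0-inf and t1/2 need

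*SAP*

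**What the plan says.** Protocol 10.1 leaves the parameter calculations to the SAP, so SAP section 4 is the governing text.

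- **Kel (SAP 4.6):** "This is the slope of the regression line when the linear regression of logarithmic concentration against time is performed for the terminal elimination phase". At least three points are needed, excluding Cmax. With two or fewer, Kel is missing.
- **AUC0-inf (SAP 4.1):** AUC0-t plus Cobs divided by Kel, where "K_{el} is the elimination rate constant of the terminal elimination phase in the elimination phase".
- **MRT0-inf (SAP 4.5):** AUMC0-inf divided by AUC0-inf.
- **t1/2 (SAP 4.7):** ln 2 divided by Kel. "It should be calculated for only subjects with a calculated" Kel.
- **Log base (SAP 7.2):** natural.
- **Summaries (SAP 8.4.2):** geometric mean and geometric CV for every parameter except tmax. The only other exception is a zero value of Cmax or an AUC.
- **Interaction ratio:** Protocol 13.3.1 uses AUC0-inf and Cmax. SAP 8.4.3 adds AUC0-last.

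For the companion point, SAP 4.1 says of AUC0-t that it "is the area under the plasma concentration-time curve from before administration to the last observation point". SAP section 4 uses "the actual elapsed time with the time of administration of the study drug at 0.00 hours for each study period". The sampling window in SAP 7.3 is "Immediately before study drug administration: Within 30 minutes before the specified time".

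**The concern.** The three rules cannot all be applied as written. A declining log-concentration line has a negative slope. Put into SAP 4.1, it subtracts the extrapolated tail instead of adding it. Put into SAP 4.7, it gives a negative half-life. MRT0-inf carries the same error, and a geometric mean of negative Kel or t1/2 values does not exist. No rule in SAP 8.4.2 covers that case.

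AUC0-inf is one of the two parameters that the protocol uses for the coadministration/monotherapy ratio and its 90% confidence interval. SAS and WinNonlin are both listed as software, without saying which one derives Kel. Someone who programmed or checked the parameters from the SAP text would not reproduce results based on a positive Kel.

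**Working it through.** The plan gives no numerical result to reproduce, so the check applies its formulas.

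**Sign.** Let ln C(t) = a + b·t over the terminal phase, with b < 0. The tail beyond the last point is the integral of Cobs·exp(b·u) over u from 0 to infinity, which equals Cobs/(-b). The half-life solves exp(b·t) = 1/2, so t = ln 2/(-b). Both formulas therefore need Kel = -b. With Kel = b, the tail becomes -Cobs/|b| and the half-life -ln 2/|b|. The log base is natural, so only the sign is at fault.

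**Inputs from the documents.** Samples are taken pre-dose and at 0.5, 1, 1.5, 2, 3, 4, 5, 6, 8, 12, 16 and 24 h (Protocol 9.2.3). The LLOQ is 0.1 µg/mL, with lower values set to 0 (SAP 7.3). The area uses the linear trapezoid (SAP 4.1). Kel uses at least three points after Cmax, with the number of points chosen by highest adjusted R² (SAP 4.6, 4.8).

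**Assumptions, not in the documents.** One-compartment oral profiles without noise, monotherapy Cmax 10 µg/mL, absorption rate constant ka 1.2/h, half-life 2.5 to 6 h.

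**Monotherapy AUC0-inf (µg·h/mL)**

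| Half-life (h) | Kel = -slope | Kel = slope | Difference |
|---|---|---|---|
| 2.5 | 56.5 | 54.7 | -3.1% |
| 3 | 64.6 | 60.6 | -6.1% |
| 4 | 81.1 | 78.1 | -3.6% |
| 5 | 96.7 | 88.9 | -8.0% |
| 6 | 112.1 | 96.7 | -13.7% |

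The difference does not rise steadily because the last quantifiable time moves from 16 h to 24 h between half-lives of 3 h and 4 h. A wider set of assumptions (half-life 3 to 8 h, Cmax 3 to 20 µg/mL) gives 1.0% to 26.8% low.

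**One ratio in full: half-life 4 h, exposure cut to 0.3, same ka.**

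- Alone: AUC0-t = 79.60, Cobs = 0.2532 at 24 h, slope = -0.1733/h, tail = 0.2532/0.1733 = 1.46. Intended 79.60 + 1.46 = 81.06; literal 79.60 - 1.46 = 78.14.
- Coadministered: the 24 h value is 0.3 × 0.2532 = 0.076, below the LLOQ, so the last point is 16 h. AUC0-t = 22.36, Cobs = 0.3038, tail = 0.3038/0.1733 = 1.75. Intended 24.11; literal 20.61.
- Ratio: 24.11/81.06 = 0.297 intended; 20.61/78.14 = 0.264 literal, a change of -11%.

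**Change in the AUC0-inf ratio over the five half-lives**

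| Exposure ratio | ka unchanged | ka halved on coadministration |
|---|---|---|
| 0.8 | 0% | -0.8% to -2.2% |
| 0.5 | 0% | -0.8% to -2.2% |
| 0.3 | 0% at 3, 5 and 6 h; -6.5% at 2.5 h; -11.3% at 4 h | -1.3% to -2.2%, except -14.8% at 4 h |
| 0.1 | -10.0% to -26.4% | -11.3% to -30.0% |

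With unchanged ka, the ratio moves only when lower exposure shortens the last quantifiable time. In the individual Kel and t1/2 ratios of SAP 4.11 the sign cancels, because both values are negative.

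**Profiles without Kel.** A very low profile (Cmax 0.12 µg/mL, ka 1.0/h, half-life 4.5 h) leaves too few points, so Kel, t1/2 and AUC0-inf are missing rather than wrong in sign. With 15% proportional error added, 40,000 simulated profiles gave one missing Kel and no positive slope.

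**Pre-dose time.** Take a zero concentration at -0.50 h. The first trapezoid is then ½ × 1.0 h × C(0.5 h) instead of ½ × 0.5 h × C(0.5 h), an excess of 0.25 h × C(0.5 h). That is 1.3% to 2.9% of monotherapy AUC0-t. With both periods sampled 30 minutes early, the AUC0-t ratio shifts by at most about 1% (largest 1.2%, half-life 2.5 h with ka halved).

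**The case against.** The strongest reply is that this is a slip of wording. The SAP calls Kel an elimination rate constant, reports it per hour, uses the standard formulas for a positive constant and asks for its geometric mean. All of that fixes the meaning as minus the slope. The SAP names a dedicated PK package, and its labels for the regression time limits suggest package output. A literal coding would show negative half-lives and AUC0-inf below AUC0-last before any ratio was reported. SAP 8.4.3 also models Cmax and AUC0-last, which do not use Kel.

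Most of this stands. It shows that the intended analysis is sound and that a wrong reported result is unlikely. It does not make SAP 4.6 correct, since no other passage supplies the sign. How the package signs its constant is not in the documents, so it cannot be relied on either way.

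It is also fair that the larger ratio shifts need a loss of 70% or more of exposure, where 0.297 and 0.264 would lead to the same conclusion. The pre-dose effect needs samples at the edge of the window and largely cancels in a crossover ratio.

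**Conclusion.** SAP 4.6 is wrong as written and should be corrected, but the fault is a missing sign and not a wrong analysis concept. Literally applied, it makes t1/2 negative and puts AUC0-inf below AUC0-t in every profile with a calculated Kel.

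A reader might infer that all profiles are affected, or that the trial's interaction result would be wrong. The documents support neither. Profiles with two or fewer eligible points have Kel and its dependents set to missing. The intended sign is clear from the surrounding text, and Cmax and AUC0-last are untouched by it.

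Under the assumed profiles, AUC0-inf would be about 3% to 14% low. The ratio would change by 0% to about 2% at exposure ratios of 0.5 to 0.8, and by more than 6% only at 0.3 or below. These sizes rest on an assumed half-life, Cmax and absorption rate; the sign error itself rests on none of them. The pre-dose point is minor: about 1% to 3% of AUC0-t at most, and about 1% or less of the ratio when both periods are sampled equally early.

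**What to change.** In SAP 4.6, write: *Kel = -1 × the slope of the linear regression of natural-log concentration on time*. SAP 4.1, 4.5 and 4.7 are then correct as they stand. In the half-life 4 h example, this gives t1/2 = ln 2/0.1733 = 4.00 h and AUC0-inf = 81.06 µg·h/mL.

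As a minor companion change, state in SAP sections 4, 4.1 and 4.4 that the pre-dose sample is assigned 0.00 h, that post-dose samples keep actual elapsed time, and that the area is integrated from 0.00 h.

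The cost is two sentences in the SAP before the data are fixed. Design, sample size and data collection do not change.

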4.7 Terminal elimination half-life: $t_{1/2}$

Unit: h

Number of display digits: Should be rounded and displayed to two decimal places.

Calculation method: $t_{1/2} = \ln(2)/K_{el}$

It should be calculated for only subjects with a calculated K_{el} . If K_{el} is not calculated, it should be regarded as a missing value and displayed as “—”.

4.8 Degree-of-freedom adjusted coefficient of determination R^2

Unit: –

Number of display digits: Should be rounded and displayed to three decimal places.

Calculation method: This is the degree-of-freedom adjusted coefficient of determination when Kel is calculated. If Kel is not calculated, it should be regarded as a missing value and displayed as “–”.

4.9 Correlation coefficient: r

Unit: –

Number of display digits: Should be rounded and displayed to three decimal places.

Calculation method: This is the correlation coefficient between logarithmic concentration and time at the time of Kel calculation. If Kel is not calculated, it should be regarded as a missing value and displayed as “–”.

4.10 Time range of the regression line used to calculate Kel:

Lambda_z_lower and Lambda_z_upper

Unit: h

Number of display digits: Should be displayed to two decimal places.

Calculation method: This is the lower (Lambda_z_lower) and upper (Lambda_z_upper) time limits of the regression line used to calculate Kel.

If Kel is not calculated, it should be regarded as a missing value and displayed as “–”.

4.11 Ratio of pharmacokinetic parameters between treatment conditions (t_{max} is the difference between the treatment conditions)

Number of display digits: Should be rounded and displayed to three decimal places. T_{max} should be rounded and displayed to two decimal places.

Calculation method: It is defined as the ratio of pharmacokinetic parameters between treatment conditions = concomitant administration / single administration (for t_{max} , difference between treatment conditions = concomitant administration – single administration). If any of the pharmacokinetic parameters is missing or has a denominator of 0, it should be regarded as missing and displayed as “–”.

5. Definition of Derived Variables

5.1 Age at consent acquisition

Age (year) = Date of consent acquisition (year) – Date of birth (year)

However, when (Date of Consent [months] < Date of Birth [months]) or (Date of Consent [months] = Date of Birth [months] and Date of Consent [days] < Date of Birth [days]), 1 is subtracted from the traditional Japanese age system calculated above.

5.2 BMI

BMI (kg/m²) = Body weight (kg) / (Height [m])²

Should be rounded and displayed to one decimal place.

6. Analysis sets

Pharmacokinetic analysis will be performed in the pharmacokinetics analysis set. Safety analysis will be performed in the safety analysis set. The analysis sets are defined below; however, details of the treatment of subjects should be determined by the sponsor by the time the data are fixed.

6.1 Pharmacokinetics analysis set

Among subjects who received at least one dose of the study drug, a population of subjects whose pharmacokinetics can be evaluated is the pharmacokinetics analysis set.

6.2 Safety analysis set

The population of subjects who received the study drug at least once is the safety analysis set.

7. Data handling

Fixed data should be handled as follows: The handling of data other than the following should be decided in the case review meeting and specified in the statistical analysis plan that will be fixed finally by the data fixation.

7.1 Definition of missing values

If test measurements are missing or if problems with samples etc. result in invalid measurements or reference values, these should be handled as missing values.

7.2 Definition of logarithmic transformation

The logarithmic transformation uses natural logarithm.

7.3 Handling of PK-related data

The permitted range of blood sampling for plasma concentration measurement is set as shown below, in consideration of the range of working hours for puncture, etc. Data outside the permitted ranges should not be imputed. Details of the acceptance or rejection of drug concentration data used for the

tabulation of drug concentration data and the calculation of pharmacokinetic parameters and the handling of other drug concentration data should be decided in the review of handling of drug concentration data and described in the final version of the statistical analysis plan.

- Immediately before study drug administration: Within 30 minutes before the specified time
- 0.5 to 16 hours after study drug administration: Within ± 5 minutes of the specified time
- 24 hours after study drug administration: Within ± 15 minutes of the specified time

(1) **Rejected data**

They will not be included in the calculation of summary statistics or pharmacokinetic parameters at each time point of blood sampling.

(2) **Plasma MT-6548 concentrations (units should be converted from ng/mL to μ g/mL)**

1) “NS”: No data

Should be treated as a missing value.

2) “<LLOQ”: Below the lower limit of quantification (0.1 μ g/mL)

Should be treated as 0.000 μ g/mL.

7.4 Handling of data at 72 hours after study drug administration

PK data, the results of measurement of general laboratory tests and vital signs, and the results of evaluations of standard 12-lead ECGs obtained immediately before administration of the study drug in Period 2 and Period 3 should not be tabulated as results obtained at 72 hours after administration of study drug in Period 1 and Period 2, respectively, but should instead be handled as data obtained immediately before administration of the study drug (i.e., baseline data) in Period 2 and Period 3, respectively. However, if data obtained immediately before administration of the study drug in Period 2 and Period 3 are judged to be adverse events compared with the baseline data in Period 1 and Period 2, respectively, they should be handled as adverse events occurring in Period 1 and Period 2.

8. Statistical Method

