Post-administration tests: These will be performed 3 days after administration of the last dose of the study drug.

Rationale

To evaluate the PK and safety of MT-6548 when MT-6548 and oral iron or iron-containing phosphate binders are coadministered in accordance with the methods of administration described in their respective package inserts, three cohorts were established: one to receive the study drug after a meal, one to receive it before a meal, and one to receive it under fasting conditions.

With reference to the draft Guideline on Drug Interactions for Drug Development and Labeling (September 4, 2017 edition), a crossover design was adopted for this study to achieve an evaluation with a high degree of accuracy in a small number of subjects. An open-label design was adopted for this study because the effects of evaluation bias are minor and PD will not be evaluated.

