9.2.4.1 Objective findings

Investigators/subinvestigators will promptly check the results and record day of confirmation and confirmation results (clinical significance) for all the following tests.

(1) General laboratory tests

The following laboratory tests will be performed on the day of screening (any time), in the evaluation period (immediately before administration of the study drug, and 24 hours after administration of the study drug in each period), and at discontinuation (only for subjects withdrawn from the study after the start of administration of the study drug, any time). The target volume of blood collected each time is approximately 2 mL for 1), 11 mL for 2), and 11 mL for 4) below, and the amount of urine to be collected is approximately 10 mL. The collection date and purpose of the blood sample will be recorded in the CRF. The study site will report the test results (excluding 4)) to the sponsor only for subjects who receive the study drug.

1) Hematology tests:

RBC count, haemoglobin, hematocrit, WBC count, platelet count, WBC fraction (neutrophils, eosinophils, monocytes, lymphocytes, basophils)

2) Blood biochemistry tests:

AST (GOT), ALT (GPT), ALP, LDH, γ -GTP, total protein, albumin, blood glucose, total cholesterol, LDL-C, HDL-C, triglycerides, total bilirubin, urea nitrogen (BUN), serum creatinine, uric acid, CPK, Na, K, Cl, Ca, P, Mg, C-reactive protein, serum iron, ferritin, TSAT

- 3) Urinalysis (qualitative)
Glucose, protein, urobilinogen, occult blood, specific gravity, pH, ketones, bilirubin
- 4) Immunology tests: Only at screening
HBs antigen, serological test for syphilis, HCV antibody, HIV antigen or antibody

(2) Vital signs (blood pressure, pulse rate, body temperature)
Blood pressure (systolic and diastolic blood pressure), pulse rate, and axillary body temperature (ascertained to the first decimal place) will be measured for subjects in the seated position on the day of screening (any time), Day -1 (day before administration of the study drug), in the evaluation period (immediately before administration of the study drug, 24 hours after administration of the study drug, and 48 hours after administration of the study drug in each period), and at discontinuation (only for subjects withdrawn from the study after the start of administration of the study drug; any time). Date and results will be recorded in CRFs.
Measurements will be made before blood sampling when possible, and after 5 minutes at rest.

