13.2 Data handling

Excluding those matters determined in the sponsor's Case Review Meeting and the Review of the Handling of Drug Concentration Data, the handling of data will be as follows.

(1) Definition of missing values

If test measurements are missing or if problems with samples etc. result in invalid measurements, these are handled as missing values.

(2) Pharmacokinetics data handling

For blood samples collected for the measurement of plasma concentration, the following time windows will be established in light of the variance in the times of venipuncture and other considerations. Data outside the allowable ranges will not be imputed. Whether or not tabulations of drug concentration data or drug concentration data used to calculate PK parameters will be included in analysis, and details of the handling of other drug concentration data will be determined in the Review of the Handling of Drug Concentration Data, and included in the Statistical Analysis Protocol.

- Immediately before administration of the study drug: Within 30 minutes before the specified time
- 0.5 to 16 hours after administration of the study drug: Within ± 5 minutes of the specified time
- 24 hours after administration of the study drug: Within ± 15 minutes of the specified time

(3) Handling of data at 72 hours after administration of the study drug

PK data, the results of measurement of general laboratory tests and vital signs, and the results of evaluations of standard 12-lead ECGs obtained immediately before administration of the study drug in Period 2 and Period 3 will not be tabulated as results obtained at 72 hours after administration of

study drug in Period 1 and Period 2, respectively, but will instead be handled as data obtained immediately before administration of the study drug (i.e., baseline data) in Period 2 and Period 3, respectively. However, if it is concluded that data obtained immediately before administration of the study drug in Periods 2 and 3 are adverse events relative to baseline in Periods 1 and 2, they will be handled as adverse events that occurred in Periods 1 and 2, respectively.

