8.1.2 Descriptive statistics to calculate

Unless otherwise specified, the following descriptive statistics should be calculated for each continuous variable item (excluding pharmacokinetic analysis).

Number of subjects, mean, standard deviation (SD), median, minimum, maximum, and 2-sided 95% CI of the mean

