8.5.4 Laboratory test values

For hematology, blood biochemistry, and urinalysis (specific gravity, pH), descriptive statistics should be calculated for each treatment condition in each cohort at each evaluation time point. The changes from baseline at each evaluation time point should be summarized in the same manner.

Concerning qualitative urinalysis (glucose, protein, urobilinogen, occult blood, ketone bodies, bilirubin), a shift table composed of frequency tabulation by category at each evaluation time point and decision results at baseline and each evaluation time point in each evaluation period should be provided for each administration condition in each cohort.

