8.5.5 Resting standard 12-lead ECG

The frequency of decision results (normal, clinically nonsignificant abnormal, or clinically significant abnormal) should be tabulated at the evaluation time point by administration condition in each cohort, and a shift table composed of the decision results at baseline and each evaluation time point should be provided.

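### Do the 72-hour safety tables lose too much by using the Period 2 and 3 pre-dose results as baseline?

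*SAP*

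**What the plan says.** SAP 7.4 deals with samples and measurements that fall 72 hours after one dose and immediately before the next. They "should not be tabulated as results obtained at 72 hours after administration of study drug in Period 1 and Period 2" but are handled as the baseline of Period 2 or Period 3. Protocol 13.2(3) has the same rule: these results "will not be tabulated as results obtained at 72 hours after administration of" the preceding dose. Both add an exception. If a pre-dose result is judged to be an adverse event against the preceding period's baseline, it counts as an adverse event of that preceding period.

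After the last dose there is no next period. Protocol 5.2 provides: "Post-administration tests: These will be performed 3 days after administration of the last dose of the study drug". That is Day 10 in Cohort 1 and Day 7 in Cohorts 2 and 3.

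Protocol 9.2.4.1 sets the laboratory times within the evaluation period as "immediately before administration of the study drug, and 24 hours after administration of the study drug in each period". Vital signs and ECG also have a 48-hour measurement in each period.

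For laboratory values, SAP 8.5.4 says that "descriptive statistics should be calculated for each treatment condition in each cohort at each evaluation time point". Unless otherwise specified, the statistics are those of SAP 8.1.2: "Number of subjects, mean, standard deviation (SD), median, minimum, maximum, and 2-sided 95% CI of the mean". For ECG, SAP 8.5.5 says that "a shift table composed of the decision results at baseline and each evaluation time point should be provided".

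**The concern.** The trial is a crossover, so one expects every subject to contribute to every condition. At 72 hours this would fail. Each condition is given last to only one group per cohort, so a 72-hour row by condition would consist of different people under each condition, and only a third or a half of those treated.

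This would matter most for laboratory tests, whose only other post-dose time in each period is 24 hours. The values for the remaining subject-periods are collected, but they appear as baseline under the following condition. A mild shift that persisted to 72 hours, short of an adverse event, would be absorbed into that baseline. At stake are the precision of the late safety summary and the reader's ability to compare conditions in it.

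**Working it through.** **Inputs.** Cohort sizes are 21, 20 and 20 (SAP 2.4: "Cohort 1: 21 subjects", and likewise for the others). They sum to 61, the protocol's total. Sequences come from the design tables in protocol 5.2 and SAP 2.2. Group sizes are not stated, so equal groups are assumed: 21/3 = 7 and 20/2 = 10. The documents give no count for a 72-hour summary, so there is no planned figure to reproduce.

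**Who is in the last period?**

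| Cohort | Condition given last, by group | Completers per condition, last period | Per condition, all periods |
|---|---|---|---|
| 1 | Group 1 ferric citrate; Group 2 sodium ferrous citrate; Group 3 alone | 7 | 21 |
| 2 | Group 4 sucroferric oxyhydroxide; Group 5 alone | 10 | 20 |
| 3 | Group 6 ferrous sulfate; Group 7 alone | 10 | 20 |

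**Precision of a 72-hour mean.** The 95% CI half-width in SD units is t(0.975, n−1)/√n:

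- Cohort 1: n = 7 gives 0.925 and n = 21 gives 0.455; ratio 2.0.
- Cohorts 2 and 3: n = 10 gives 0.715 and n = 20 gives 0.468; ratio 1.5.

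**Comparing changes from baseline.** The plan does not do this, but a reader might. Assume a subject effect plus independent errors of variance s². A change from the period's own baseline has variance 2s².

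- *Last period only.* Two separate groups are compared. The variance is 2s²/7 + 2s²/7 = 4s²/7 in Cohort 1 and 4s²/10 in Cohorts 2 and 3.
- *All periods.* In adjacent periods the middle value is both the 72-hour result of one and the baseline of the next. The difference of changes is Y2 − 2Y1 + Y0, with variance (1 + 4 + 1)s² = 6s². In non-adjacent periods it is 4s². For each combination against MT-6548 alone in Cohort 1, two groups are adjacent and one is not, so the average is (6 + 6 + 4)/3 = 16/3. The variance is (16/3)s²/21 in Cohort 1 and 6s²/20 in Cohorts 2 and 3.
- *SE ratio.* Cohort 1: √[(4/7)/((16/3)/21)] = √2.25 = 1.50. Cohorts 2 and 3: √[(4/10)/(6/20)] = 1.15.

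The shared value costs much of what the extra subjects would bring: adjacent changes have correlation −s²/(2s²) = −0.5.

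**Seeing a rare abnormality.** The chance of at least one among n is 1 − (1 − p)^n. The rates p are assumed.

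| p | n = 7 | n = 21 | n = 10 | n = 20 |
|---|---|---|---|---|
| 5% | 30% | 66% | 40% | 64% |
| 10% | 52% | 89% | 65% | 88% |

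**Does the row exist?** Protocol 9.2.4.1 names screening, pre-dose, 24 hours (plus 48 hours for vital signs and ECG) and discontinuation. It names no 72-hour or post-administration measurement. The schedule tables do have a 72-hour column after the last period, but their cells cannot be read reliably in the text available. The SAP's contents page announces a list of output tables that this text does not contain. The counts above are therefore conditional on such a row being produced.

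**The case for a change.** The best case for a change is that it needs no new measurement. The Day 4 and Day 7 values exist, the laboratory panel includes iron indices and liver enzymes, and a supplementary table could show each value as a change from the preceding period's own baseline while leaving the baseline and adverse event rules alone. The adverse event exception catches only findings judged clinically significant, so milder 72-hour shifts would be summarised for a fraction of the subjects.

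The counts and half-widths stand, and the table would add some information. If the post-administration tests turned out to omit these measurements, the pre-dose values would be the only 72-hour data (14 of 21 or 10 of 20 per condition).

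The rest carries less weight:

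- The groups are randomised and all last-period values come from the same period. Comparing conditions there is an ordinary randomised parallel comparison, less precise but not systematically unbalanced.
- The pre-dose values are not hidden. They are displayed as baseline.
- The minimum remedy, showing n, is already planned. The number of subjects is a listed statistic in protocol 13.3.2 and SAP 8.1.2, and the shift tables show counts.
- Using one value twice brings its own awkwardness: it appears in two rows, and adjacent changes are negatively correlated by construction.

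**Conclusion.** No change is needed. A value taken just before a dose has to be given a role, and the plan gives it one in advance, identically in the protocol and the SAP, with an exception that protects adverse event reporting. Following the rule gives sound results. Every period contributes to the 24-hour summaries and to the 48-hour vital signs and ECG, safety is described without any between-condition contrast, and pharmacokinetic sampling ends at 24 hours.

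The cost is confined to one descriptive row, if it is produced: 7 instead of 21 or 10 instead of 20 completers per condition, a mean whose interval is 2.0 or 1.5 times as wide, and an SE ratio of 1.50 or 1.15 for a comparison of changes that nobody plans. These figures rest on equal groups, on post-administration tests that include the measurements, and, for the SE ratios, on independent errors.

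This is a fair trade-off on which statisticians may differ. An analyst who produces the row may add a footnote that it holds last-period completers, but no conclusion of the trial depends on it.
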